### **2.1. Sample Size Considerations**

Sample size calculations are based on 80% Power, using a two-sided Pearson's Chi-square Test for Proportion Differences at the 5% significance level. It is estimated that between 60% and 70% of hospitalized patients with mild or severe disease will improve clinically and become ambulatory after standard treatment (WHO ordinal scale score 1-2 Fig.2)). Table 1 presents the sample sizes that are required in each treatment group to detect a significant difference in the percent of hospitalized patient leading to an ambulatory disease (shift from category 5-8 to category1-2 in 20%, 25%, 30% or 35% of hospitalized patients after treatment with estradiol (E2) and progesterone (P4)). Efforts will be made to recruit 60 patients in each treatment group in order to stratify by disease severity, age and gender.

Table 1.		
Treatment	Percent leading to a scale 1-2	Sample Size
SOC	60%	32
SOC + E2 + P4	90%	32
SOC	60%	22
SOC + E2 + P4	95%	22
SOC	70%	62
SOC + E2 + P4	90%	62
SOC	70%	36
SOC + E2 + P4	95%	36

An interim analysis will be performed at 50% enrollment to determine to what extent a strong treatment efficacy warrants stopping the trial early. Table 2 presents interim sample sizes and required Z test statistics for comparing two proportions at each of stage of a O'Brien-Fleming alpha-spending sequential design (24). Based on 80% power and an overall 5% significance level, if the interim analysis for the first 60 enrolled patients results in differences that are more than 2.96 standard deviations from 0, the trial will end, and treatment efficacy will be concluded. Otherwise, the trial will enroll the total 120 patients.

Table 2.			
	Treatment	Sample Size	Standardized Z test Statistic
Stage 1	SOC	30	2.96
	SOC + E2 + P4	30	
Stage 2	SOC	60	1.96
	SOC + E2 + P4	60	

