### **3.1 Collection of blood samples**

The collection of routine blood samples and patient monitoring will be conducted as part of the standard of care procedures that are utilized at the hospital for COVID-19 patients. The collection of blood samples (CBC with differential, blood chemistry, inflammation markers) is to monitor disease severity and is independent from this protocol, but we will use the data in our analysis as explained in section 3.5. Women of childbearing age will have a pregnancy test on admission

An additional blood sample will be collected for our study at admission and after 5 days of treatment. We will collect about 1-5 teaspoons of blood at these two time points. This blood sample will be stored in [name] lab for 1) isolation of peripheral blood mononuclear cells (PBMC) to assess the effect of treatment on immune cells populations by flow cytometry and PBMC gene expression by RNA-Seq 2) and metabolomics profiling to determine metabolic and molecular signatures of the efficacy of treatment. De-identified serum and PBMC frozen samples will be transferred to the University of Michigan Metabolomics Core to perform untargeted metabolomic analyses. University of Michigan will not receive identifiable information nor a link to identifiers related to the samples.

Additionally, we propose to use the serum and PBMC from our collected blood samples to perform multi-dimensional analysis in the Center for Translational Research in Infection and Inflammation (Collaboration with [name]), and the laboratories of [name] and [name] at Tulane University School of Medicine. Blood samples will be stored for up to 3 years.

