### **3.3 Outcome Measures**

For all randomized patients according to section 2.2, demographic and clinical variables, including sex, age, race/ethnicity, BMI, symptoms, vital signs (blood pressure, respiratory rate, temperature, oxygen saturation), chronic comorbidities through diagnosis codes, medications, clinical course during hospitalization (described in primary outcome below) will be reviewed in the patients' medical charts. Laboratory measurements including when available CBC, blood chemistry, liver function test, creatinine, BUN, lactate, troponin, ferritin, CRP, procalcitonin, Brain-type natriuretic peptide, D-dimer, interleukin-6, G6PD. We will review the participants' medical records for up to 6 months after hospital discharge.

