#### **Primary outcome:**

For all randomized patients with baseline inclusion criteria, WHO ordinal scale score 3-5, the primary efficacy end point will be the proportion of patients who achieve scores 1 or 2 on the 9-point World Health Organization (WHO) ordinal scale (Fig. 2) through day 28.

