#### **Secondary outcomes:**

For all randomized patients, the following secondary end points will be assessed at day 14, 28 and 60

1. Length of hospital stay
2. Duration of mechanical ventilation
3. Cause of death and number of days death occurred after admission
4. Readmission
5. Change in biological markers below between admission and occurrence of primary endpoint (2 values at least 2 days apart)
6. Grade 3 and 4 adverse events
  
7. Serious adverse events

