#### ***Biological markers***

Obtained from Standard Of Care: *Inflammation:* neutrophil:lymphocyte ratio, C-reactive protein, ferritin, procalcitonin.

*Hypercoagulability:* D-dimers, fibrinogen

*Tissue injury:* troponin, ALAT, ASAT, LDH

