**Ordinal Scale for Clinical Improvement**

Patient State	Descriptor	Score
Uninfected	No clinical or virological evidence of infection	0
Ambulatory	No limitation of activities	1
	Limitation of activities	2
Hospitalized Mild disease	Hospitalized, no oxygen therapy	3
	Oxygen by mask or nasal prongs	4
Hospitalized Severe Disease	Non-invasive ventilation or high-flow oxygen	5
	Intubation and mechanical ventilation	6
	Ventilation + additional organ support – pressors, RRT, ECMO	7
Dead	Death	8

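### Secondary outcome 5 ends marker change at the primary endpoint event, so it has no defined end for patients who never recover and a recovery-dependent interval for those who do

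*Combined protocol and SAP*

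**What the plan says.** The lead-in to the secondary outcomes in section 3.3 reads "For all randomized patients, the following secondary end points will be assessed at day 14, 28 and 60". Item 5 of that list is "Change in biological markers below between admission and occurrence of primary endpoint (2 values at least 2 days apart").

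The primary endpoint, in the same section, is "the proportion of patients who achieve scores 1 or 2 on the 9-point World Health Organization (WHO) ordinal scale" through day 28. On the scale in Figure 2, scores 1 and 2 are the ambulatory states, and the first hospitalised state, score 3, is "Hospitalized, no oxygen therapy". Section 2.1 expects that "between 60% and 70% of hospitalized patients with mild or severe disease will improve clinically and become ambulatory after standard treatment".

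The routine markers (inflammation, hypercoagulability, tissue injury) are "Obtained from Standard Of Care", and section 3.3 introduces the chart review with "Laboratory measurements including when available CBC, blood chemistry" and other tests. The marker list below item 5 continues with the metabolome, proteome and PBMC. For the research samples section 3.1 says "An additional blood sample will be collected for our study at admission and after 5 days of treatment".

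Section 3.4 compares marker change between arms with a two-sample t test or Mann-Whitney test, then with multiple linear regression. It gives no rule for patients without the endpoint and does not name interval length as a covariate.

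**The concern.** A change score needs a start and an end that exist for every patient analysed. Here the end is a clinical success.

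- **Patients without the event.** Someone who dies or stays at score 3 or above through day 28 has no end point under item 5. Someone who reaches score 1 or 2 within 2 days of admission cannot supply the required pair of values.
- **Patients with the event.** The second value falls whenever recovery happens. If treatment speeds recovery, the two arms are measured over different lengths of time.

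The comparison is therefore between patients selected after randomisation, over intervals that treatment may alter. The markers bear on the trial's proposed mechanism, damping the cytokine storm. An analyst who has to choose the second value after the data are in could reach different answers from the same charts.

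Item 5 also collides with section 3.1. Read literally, the metabolome, proteome and PBMC measures end at the endpoint event too, although their second sample is drawn after 5 days of treatment.

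**Working it through.** **1. The plan's own figures.** Table 1 (section 2.1) reproduces with the pooled-variance formula for two proportions, two-sided 5%, 80% power, no continuity correction. For 70% v 90%:

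n = [1.96 × √(2 × 0.8 × 0.2) + 0.8416 × √(0.7 × 0.3 + 0.9 × 0.1)]² / 0.2² = 1.5697² / 0.04 = 61.6, so 62.

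The other pairs give 32, 22 and 36, as printed. The documents give no figure for item 5 itself.

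**2. Patients with no defined end point.** Count = 60 × (1 − response rate).

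| Arm | Rate | Count |
|---|---|---|
| Control | 60% | 60 × 0.40 = 24 |
| Control | 70% | 60 × 0.30 = 18 |
| Treated | 90% | 60 × 0.10 = 6 |
| Treated | 95% | 60 × 0.05 = 3 |

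That is 18 + 3 = 21 to 24 + 6 = 30 of 120 (17.5% to 25%). With an assumed gain of only 10 points the split is 24 v 18 or 18 v 12. With no gain it is equal.

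**3. The interval for responders.** The minimum is 2 days (item 5) and the maximum 28 days (primary outcome).

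**4. One illustration of the interval effect.** None of these inputs is in the documents: a log marker falling on average 0.12 a day in both arms (no true effect); lognormal time to endpoint with median 6 days treated and 8 days control, log-SD 0.4 to 0.6, limited to 2 to 28 days. Spurious difference = 0.12 × difference in mean interval.

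- Steady fall, log-SD 0.4: mean intervals 6.50 and 8.66 days, so 0.12 × 2.16 = 0.26.
- Steady fall, log-SD 0.6: mean intervals 7.17 and 9.44 days, so 0.12 × 2.27 = 0.27.
- Fall stops at day 5, log-SD 0.4: mean days of fall 4.65 and 4.90, so 0.12 × 0.25 = 0.03.
- Fall stops at day 5, log-SD 0.6: 4.43 and 4.72, so 0.12 × 0.29 = 0.035.

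Simulation with 54 v 42 responders gives 0.26 to 0.28 and 0.03 to 0.04. In these cases the faster-recovering arm shows the smaller fall. With equal recovery times the difference is about zero and the test keeps its level.

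**5. Why the direction is not fixed.** Suppose instead that every patient recovers once the log marker has fallen by 0.96. Falls of 0.16 v 0.12 a day mean recovery at 0.96/0.16 = 6 days v 0.96/0.12 = 8 days. Both arms show a change of 0.96, so a real difference in speed is invisible.

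**6. Does other text fill the gap?**

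- *The lead-in's days 14, 28 and 60.* These do not fit an event-driven end, and no blood draw is described at those days. Section 3.1 has routine inpatient sampling plus research draws at admission and day 5. Figure 1's entries at days 28 and 60 are side-effect and symptom checks. Day 60 follow-up is in person or by telephone (section 3.3, safety), and section 6 describes the last visit as by telephone.
- *The 2-day condition.* It sets a minimum gap and does not say which values to use.
- *Section 3.4.* It names tests and regressions only.

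**The case against.** The strongest reply is that patients without the endpoint are mostly still in hospital and having routine bloods, and records are reviewed for up to 6 months after discharge. On that view the 2-day condition is the working rule: take any two chart values far enough apart. It stands in part. A reader might infer from the counts that 18 to 24 control patients would have no marker data, and the documents do not support that. The counts are patients without the endpoint event at the planning rates. What is missing is the rule for choosing the second value.

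A second reply reads the end point as the day 28 assessment. That would remove the problem, but the wording describes an event that is achieved through day 28, and no day 28 blood draw is described.

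A third is that the planned regression could adjust for interval length. The plan does not name it as a covariate. Adjustment would not fully cure the problem either, because interval length is itself a result of recovery after randomisation.

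Finally, this is one of seven secondary outcomes, and every input to the bias illustration is assumed. That stands, and it limits the weight of the point.

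**Conclusion.** The definition of item 5 is faulty as written. It cannot be computed for every randomised patient, although the list says it applies to all of them, and for responders its interval is set by recovery. Confidence is high on that, because it follows from the text.

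The size rests on two different footings. The counts, 18 to 24 control v 3 to 6 treated, use only the plan's rates and 60 per arm, and the imbalance vanishes if treatment does not change response. The bias figures rest wholly on assumed inputs and run from about zero to 0.28 log units.

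A reader might infer that the marker result will be biased, or biased in a known direction. The documents do not support either. If treatment changes neither response nor its timing, the test keeps its level. Nor does the point reach the primary analysis or Table 1, which do not use item 5. It would also be wrong to treat the metabolome, proteome and PBMC measures as exempt: they sit in the list that item 5 refers to, so items 5 and section 3.1 need to be reconciled.

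This should be corrected, in proportion to a single secondary outcome.

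**What to change.** Redefine item 5 as the change in each marker from admission to day 5 in all randomised patients, regardless of clinical response.

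- For routine markers, use the standard-of-care value nearest day 5 within a stated window, for example days 4 to 6.
- For the metabolome, proteome and PBMC measures, use the day-5 research sample already planned.
- Allow stored day-5 serum as a fallback only for markers measurable in serum. It cannot supply the neutrophil:lymphocyte ratio or fibrinogen.
- Compare arms adjusting for the admission value, on the log scale for skewed markers.
- State in advance how deaths and discharges before the window are handled, and report missing values by arm and reason.
- State whether the lead-in's days 14, 28 and 60 apply to item 5.

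The cost is protocol and analysis wording, plus some assay cost if the serum fallback is used.

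The drawback is that day-5 values will be missing for early discharges, possibly more often in the faster-recovering arm. Under the same assumed recovery times, 15.5% to 25.0% of treated and 4.2% to 12.4% of control responders recover before day 4. That is about 8 to 14 of 54 v 2 to 5 of 42. A fixed day reduces the dependence on recovery time but does not remove it.

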## 1. Study aim, background, and design

Coronavirus SARS-CoV-2, causing COVID-19, has infected over 20 million people and killed over 700,000 as of August 2020. Although, the vaccination campaign is ramping up, vaccination hesitancy in the United States represents up to 25-30% of the population (1), and hospitalizations and deaths are still at the level of 2020. Apart from corticosteroids (2), most available therapeutic options are at best marginally efficient in reducing disease severity and mortality and extremely expensive (3-5). Therefore, the systematic investigation of clinically approved drugs is a priority in order to determine what does improve the disease and invest resources to go to full-scale production. Our current understanding of the disease is that COVID-19 deaths result from an inappropriate immune response with outpouring of pro-inflammatory chemokines leading to lung infiltration and hyperactivation of monocytes and macrophages producing pro-inflammatory cytokines (cytokine storm), resulting in lung edema, reduced gas exchange, and ultimately leading to acute respiratory distress syndrome and multiorgan failure (1-8). *Men with COVID-19 have a uniformly more severe outcome than women.* In series from China, Europe and the U.S., COVID-19 mortality was consistently 1.5 to 2-fold higher in men than in women, suggesting that female biological sex is protecting women from COVID-19 mortality (9-13). It is established that women exhibit heightened immune responses to viral infections compared to men (14), which is at least partially due to the genetic benefit of gene dosage in X-linked immune-response genes. Ovarian steroids, however, also play a protective role. In New York City, among 5700 hospitalized patients, the female protection from COVID-19 mortality was observed at all ages, but was more pronounced in subjects under 50 years of age (18% mortality in women) compared to patients > 50 years of age (40.5% mortality in women) (13), suggesting that ovarian steroids are involved in mitigating COVID-19 mortality in pre-menopausal women. Further, the analysis of electronic health records of over 68,000 COVID-19 patients revealed that estrogen therapy is associated with more than 50% reduction in mortality (15). The main female steroids, 17 $\beta$ -estradiol and progesterone exhibit potent immuno-modulatory and anti-inflammatory actions via estrogen and progesterone receptors expressed in all immune cells, including epithelial cells, macrophages, dendritic cells, CD4+ and CD8+ lymphocytes, and B cells (14,16). Progesterone also acts partially via the glucocorticoid receptor. Together estradiol and progesterone produce a state of *decreased innate immune cells production of proinflammatory cytokines, enhanced T cells anti-inflammatory responses and immune tolerance, and enhanced B-cell-mediated antibody production* (14,17,18). The National Institutes of Health (NIH) COVID-19 Treatment Guidelines Panel recommends the use of dexamethasone 6 mg per day for up to 10 days or until hospital Discharge (whichever comes first) as standard of care (SOC) for the treatment of hospitalized COVID-19 patients who require supplemental oxygen but who are not mechanically ventilated and for the treatment of hospitalized patients who are mechanically ventilated. Remdesivir is SOC at Tulane for COVID-19 patients who require supplemental oxygen but who are not mechanically ventilated. We believe that in hospitalized COVID-19 patients, a short treatment with the combination estradiol and progesterone, administered early and as a prevention in addition to SOC, will prevent or mitigate the cytokine storm while increasing antibody production and prevent severe outcomes, without side effects (18). Therefore, it will provide steroid immunomodulation without immunosuppression. The advantage of repurposing estradiol and progesterone compounds is the depth of knowledge regarding their clinical efficacy and toxicity that has accumulated from decades of clinical and basic studies. Estradiol and progesterone are widely available in hospitals, inexpensive, manufacturable to scale, and can be prescribed immediately. Please note there is no increased risk of blood clot following acute and systemic administration of natural hormones. The risk exists following chronic and orally administered synthetic hormones (as discussed below).

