No member of the DSMB will have direct involvement in the conduct of the study. The DSMB will review and evaluate the accumulated study data for participant safety, adverse events, study conduct, progress, adherence to the protocol and efficacy. The DSMB will consider study-specific data as well as relevant background knowledge about COVID-19, estrogen and progesterone therapy, and the patient population under study. The data will remain blinded. The frequency of DSMB meetings will depend on the rate of enrollment but will roughly occur quarterly. The DSMB meetings will be private and closed meetings. [name] will be responsible for convening meetings by conference calls or Zoom videoconferences or as face-to-face meetings, and coordinating the distribution of meeting materials to DSMB members. The written open session reports from DSMB meetings will be submitted to the Tulane IRB.

We will implement a group sequential trial framework with the option for stopping for safety or harm with an early interim look once 30 patients finish the Day 28 assessment. This will allow the DSMB to evaluate trial safety data. A decision about study continuation will be made based on the independent DSMB recommendations. The DSMB will convene if study participants experience a higher rate than the background rate of thromboembolic disease. The DSMB will also convene when  $\geq$  Grade 3 AE are observed and considered related to drug or not.

We will follow-up in person or by telephone for all subjects in your trial for any adverse events/serious adverse events (AEs/SAEs) and mortality at Day 60.

Adverse events will be graded according to Common Terminology Criteria for Adverse Events (CTCAE) Version5 and taken care with the corresponding specialized clinical management of the SAE.

Grade 1 adverse events (asymptomatic or mild symptoms; clinical or diagnostic observations only; intervention not indicated) or Grade 2 adverse events (moderate; minimal, local or noninvasive intervention indicated; limiting age-appropriate instrumental activity of daily living): such as breast tenderness, nausea, vomiting, bloating, stomach cramps, headaches, vaginal itching, abnormal uterine bleeding will not require discontinuation of treatment.

Grade 3 (severe) like DVT and 4 (life-threatening) serious adverse events such as MI, stroke, POME, anaphylaxis will be managed by treatment discontinuation (except SOC) and appropriate specialized clinical management of the SAE.

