## **4. Risks**

This is a greater than minimal risk study due to the new investigational use of an FDA-approved drug in this study. IM injection may cause some swelling and tenderness at the injection site. The side effects of estradiol includes breast tenderness. The side effects of progesterone include vaginal bleeding. In

addition, drawing blood from a vein may cause local pain, bruising, occasional lightheadedness, dizziness, fainting, and very rarely, infection at the site of the blood draw. To reduce risk of anxiety or pain related to the blood draw, experienced nurses or phlebotomists will draw blood.

The risk of deep vein thrombosis (DVT) or pulmonary embolism associated with estradiol and progesterone treatment exists but is minimal. First, the risk of DVT is associated with chronic hormone therapy, over months, not acute hormone therapy of several days. Most importantly, the risk is minimal because of parenteral estradiol administration, which does not alter clotting factors. DVT risk occurs mainly following orally administered estrogens and synthetic progestin because of first-pass liver metabolism leading to high liver exposures to hormones that increase hepatic production of clotting and inflammatory factors (19). Additionally, the DVT risks are usually associated with the use of conjugated equine estrogens (Premarin) alone or associated with a synthetic progestin like medroxyprogesterone acetate (Prempro) (19). There is no documented risk with natural hormones estradiol given systemically (IM, SC) and no documented risk with the use of progesterone. Additionally, most COVID-19 patients are at risk of DVT and will be placed on prophylactic anticoagulants at admission as Tulane SOC.

There is a risk of breach of confidentiality. In order to minimize this risk, all data will be de-identified and minimal PHI will be gathered (i.e., medical record number). Maintaining a link between the study ID number and medical record number is important to prevent a given chart being entered twice in the database. PHI will be stored securely in REDCap and separately from the study dataset.

A schedule of risk assessment is shown on Fig.1

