**Figure 1. Schedule of safety assessments**

Surveillance	Days following initiation of treatment								
	0	1	2	3	4	5	7	28	60
Pregnancy test*	X								
Injection site		X	X	X	X	X	X		
E2 side effects		X	X	X	X	X	X	X	
P4 side effects		X	X	X	X	X	X		
DVT symptoms		X	X	X	X	X	X	X	X
MI symptoms		X	X	X	X	X	X	X	X
Stroke symptoms		X	X	X	X	X	X	X	X
Fluid retention**		X	X	X	X	X	X	X	X

\* Women in reproductive age

\*\* Patients with renal impairment

Figure 2. Adapted from WHO R&D Blueprint Feb 18, 2020, Geneva, Switzerland

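### Adverse-event outcomes stop at Grade 3-4 and SAEs and Section 3.4 specifies no adverse-event analysis, so no by-arm comparison of the expected, mostly Grade 1-2 hormone side effects is prespecified

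*Combined protocol and SAP*

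**What the plan says.** **Outcomes.** Section 3.3, Secondary outcomes, says that for all randomized patients "the following secondary end points will be assessed at day 14, 28 and 60". Of the seven items, two concern adverse events: item 6, "Grade 3 and 4 adverse events", and item 7, "Serious adverse events".

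**Expected effects.** Section 4 (Risks) mentions swelling and tenderness at the injection site and then states: "The side effects of estradiol includes breast tenderness. The side effects of progesterone include vaginal bleeding".

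**Grading.** Safety measures and monitoring adopts CTCAE Version 5. It says that Grade 1 or Grade 2 events "such as breast tenderness, nausea, vomiting, bloating, stomach cramps, headaches, vaginal itching, abnormal uterine bleeding will not require discontinuation of treatment". The same section gives DVT as an example of Grade 3, and MI, stroke, POME and anaphylaxis as examples of Grade 4.

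**Collection.** That section also provides for daily monitoring of the Section 4 events in all randomized patients, and for a Day 60 contact about any AE or SAE and mortality. Figure 1 has rows for injection site, "E2 side effects" and P4 side effects.

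**Analysis.** Section 3.4 names tests for the primary outcome, readmission, length of stay and biological markers. It promises a general summary by arm of clinical outcomes and demographics. Adverse events are not mentioned.

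**Background.** Section 1 gives the investigators' belief that the combination will "prevent severe outcomes, without side effects".

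**The concern.** The plan names the side effects it expects, presents most of them as low-grade, schedules their collection, and then sets its adverse-event outcomes above that level. A patient whose only event is Grade 1-2 breast tenderness or uterine bleeding, and not serious, counts under neither item 6 nor item 7.

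The trial gives hormones to men and to pre- and postmenopausal women, and its rationale includes an absence of side effects. If the safety report follows the outcome list alone, the two arms could look alike on adverse events while the commoner, expected effects differ. What is at stake is the safety description of the treatment, not the primary efficacy result.

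**Working it through.** **1. Trace each expected effect through the plan.**

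| Event | Named as expected | Grade in Safety measures and monitoring | Figure 1 marks | Counts in item 6 or 7? | Analysis in Section 3.4 |
|---|---|---|---|---|---|
| Injection-site swelling, tenderness | Section 4 | Not graded | Days 1-5, 7 | Only if Grade 3-4 or serious | None |
| Breast tenderness (estradiol) | Section 4 | Grade 1-2 example | E2 row: Days 1-5, 7, 28 | Only if Grade 3-4 or serious | None |
| Vaginal or uterine bleeding (progesterone) | Section 4 | Grade 1-2 example | P4 row: Days 1-5, 7 | Only if Grade 3-4 or serious | None |
| DVT, MI, stroke | DVT in Section 4 | Grade 3-4 examples | Days 1-5, 7, 28, 60 | Yes | None |

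Figure 1 does not define its E2 and P4 rows. Breast tenderness and bleeding are placed in them from Section 4. Where nausea, headache or vaginal itching would be recorded is not stated.

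Two things follow. The low-grade effects are collected but sit in no outcome. The last column is empty throughout, so Section 3.4 gives no method even for items 6 and 7.

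**2. Compare the time windows.** Figure 1 ends injection-site and P4 checks at Day 7 and E2 checks at Day 28, and none of the three is marked at Day 60. Safety measures and monitoring asks about any AE at Day 60. The secondary outcomes are assessed at Days 14, 28 and 60, but Figure 1 has no Day 14 column. The window for counting an event is therefore not settled.

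**3. What a by-arm table could show.** The plan states no figure to reproduce here. The only input from the documents is 60 per arm (Section 2.1). The side-effect rates are assumptions, chosen to span a range.

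For x of n patients with p = x/n and z = 1.96, the Wilson limits l and u are

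[p + z²/2n ± z·√(p(1−p)/n + z²/4n²)] / (1 + z²/n).

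The Newcombe 95% CI for d = p1 − p2 runs from d − √[(p1−l1)² + (u2−p2)²] to d + √[(u1−p1)² + (p2−l2)²]. The p-value is from Fisher's exact test, two-sided.

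Example, 18/60 v 6/60: the Wilson limits are 0.199 to 0.425 and 0.047 to 0.202.
- Lower limit: 0.20 − √[(0.300−0.199)² + (0.202−0.100)²] = 0.057.
- Upper limit: 0.20 + √[(0.425−0.300)² + (0.100−0.047)²] = 0.336.

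| Assumed rates | Patients | Difference (points) | 95% CI (points) | Fisher p |
|---|---|---|---|---|
| 30% v 10% | 18 v 6 | 20 | 6 to 34 | 0.011 |
| 20% v 5% | 12 v 3 | 15 | 3 to 27 | 0.025 |
| 15% v 5% | 9 v 3 | 10 | −1 to 22 | 0.13 |
| 10% v 5% | 6 v 3 | 5 | −5 to 16 | 0.49 |

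In the first two rows, 24 (18 + 6) and 15 (12 + 3) patients would have an event. If all were Grade 1-2 and not serious, none would count under item 6 or 7.

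**4. Denominator for sex-specific events.** If half the patients were women (an assumption), a 20% uterine-bleeding rate in women would appear as 0.20 × 0.5 = 10% of all randomized patients. A new table should therefore state its denominators.

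**The case against.** **The list of secondary end points does not limit what may be tabulated.** Adverse events are monitored daily, graded, reviewed by the DSMB and asked about at Day 60, and Section 3.4 summarizes clinical outcomes by arm. This stands in part. A reader might infer that these effects will never be compared or reported, and the documents do not say that. They only prespecify no comparison. The DSMB review does not fill the gap, because the plan says the data stay blinded and describes no between-arm comparison.

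**CTCAE grade follows severity, not event type.** This stands. A reader might infer that items 6 and 7 shut out hormone side effects by definition. They do not: bleeding or vomiting that reached Grade 3, or was serious, would count. The Grade 1-2 list is given by example, and it appears in a rule about treatment discontinuation.

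**No tolerability conclusion is planned.** This also stands. A reader might infer that the trial's tolerability conclusion is bound to be wrong. The stated purpose concerns severity of symptoms and outcomes, and the phrase about side effects is a belief in the background. Section 4 lists side effects openly, and the outcomes do cover the serious harms named. Focusing on Grade 3-4 events and SAEs in hospitalized COVID-19 patients is defensible as an emphasis.

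**The differences may be small.** With one injection and five days of progesterone, they could be below what 60 per arm can resolve, as the last two rows of the rate table show. This is a reason to read the table descriptively, not to omit it.

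**Conclusion.** The concern holds as a gap in prespecification. The adverse-event outcomes stop at Grade 3-4 and SAEs, Section 3.4 specifies no adverse-event analysis of any grade, and the expected, mostly Grade 1-2 effects are collected without a planned by-arm comparison. The planned safety outcomes therefore cannot support or contradict the background statement for these events.

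The size cannot be derived from the documents, which give no side-effect rates. Under the assumed rates and full enrollment of 60 per arm, differences of 15 to 20 points would be distinguishable, and differences of 5 to 10 points would not. The finding that nothing is prespecified rests on the text alone and on none of those rates. This is a worthwhile, low-cost improvement. It leaves the primary endpoint and its analysis untouched.

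**What to change.** 1. **Section 3.3, outcome 6.** Change it to adverse events of any grade, by CTCAE grade, keeping Grade 3-4 as a subset.
2. **Section 3.4.** Add a descriptive table by arm with the number and percentage of patients with any adverse event by grade, with SAEs, and with each Figure 1 side-effect item, each with risk difference and 95% CI. State the safety population and the counting window. Use women as the denominator for uterine bleeding and vaginal itching, and show breast tenderness by sex.
3. **Figure 1 and Safety measures and monitoring.** Reconcile the collection windows (Day 7 or Day 28) with the Day 60 contact for any adverse event, and state which events the E2 and P4 rows cover.

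The cost is plan wording and one table, largely from data already scheduled for collection. The downside is more safety comparisons, some with few events, so the table should be labelled descriptive. None of this touches dosing, discontinuation or other clinical management.
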